2.2. Secondary Objectives and Endpoints

To evaluate safety and tolerability of hepatic ultrasound insonification in subjects with T2DM, assessed by:

- Incidence and severity of adverse device effects (ADEs) [including, liver injury]
- Incidence and severity of clinically significant laboratory abnormalities
- Change from baseline in vital signs (blood pressure, temperature, respiratory rate, and heart rate)
- Incidence and severity of clinical findings on physical examination
- Change from baseline in 12-lead electrocardiogram (ECG) parameters; the primary ECG endpoint will be QTcF

To evaluate the effect of hepatic ultrasound insonification on changes from baseline in whole-body insulin sensitivity during a two-step hyperinsulinemic, euglycemic clamp (HE Clamp), assessed by:

- Insulin Sensitivity Index (SI)

- Glucose disposal rate during steady state (M)
- Glucose metabolic clearance rate during steady state (MCR)

To evaluate the effect of hepatic ultrasound insonification on change from baseline in glucose tolerance and insulin secretion, assessed by an oral glucose tolerance test (OGTT)

- Area under the curve (AUC), total and incremental time, e.g., $AUC_{0-180\text{min}}$

To evaluate the effect of hepatic ultrasound insonification on glucose metabolism parameters, assessed by:

- Change from baseline in blood glucose (BG) profiles assessed with continuous glucose monitoring system (CGMS)
 - Time spent in defined glucose ranges
 - Average daily glucose
 - BG variability parameters (e.g., coefficient of variation as percentage of mean level [% CV], etc.)
 - Low blood glucose index (LBGI)
 - High blood glucose index (HBGI)
- Change from baseline in Homeostasis Model Assessment of Insulin Resistance (HOMA-IR)
- Change from baseline in Homeostatic Model Assessment of Insulin Secretion (HOMA-B)
- Change from baseline in fasting plasma glucose (FPG)

2.3.Exploratory/Other Objectives and Endpoints

To evaluate the effect of hepatic ultrasound insonification on glucose/metabolism parameters, assessed by:

- Change from baseline in exploratory biomarkers (blood samples will be stored for potential later analysis), e.g., but not limited to:
 - Glucagon
 - Glucagon-like peptide 1 (GLP-1), total
 - Leptin
 - Ghrelin
- Change from baseline in long-term glucose parameters
 - Hemoglobin A1c (HbA1c)
 - Fructosamine
- Change from baseline in lipid metabolism parameters
 - Free fatty acids (FFAs)
 - Triglycerides (TG)
 - Total cholesterol
 - Low-density lipoprotein (LDL-C)
 - High-density lipoprotein (HDL-C)
 - Very low-density lipoprotein (VLDL-C)

[figure not shown]
- Change from baseline in inflammatory biomarkers (blood samples will be stored for potential later analysis), e.g., but not limited to:
 - Cytokines (IL-6)
 - Adiponectin
 - C-reactive protein (CRP)

3. STUDY DESIGN

3.1. Experimental Design

This is an open label, exploratory pilot study to assess the effects of hepatic ultrasound insonification on glucometabolic parameters in subjects with T2DM through selective hepatic ultrasound of the porta hepatis region of the liver utilizing pulsed ultrasound.

Figure 1. Study Design Schematic

*Screening Period will be extended for at least 30 days, for subjects with $BMI > 35.0$ and $\leq 40.0 \text{ kg/m}^2$ and/or waist circumference > 40 and ≤ 45 inches.

Assessments will be performed via CGMS, OGTT, H-E clamp with stable isotope labeled glucose ($[6,6-2\text{H}_2]$ glucose), measurements of insulin secretion and resistance (e.g. HOMA-IR), change in glucose parameters, inflammatory biomarkers and potential analysis of exploratory biomarkers.

The study (Fig. 1) will be conducted in 1 cohort, enrolling approximately 15 subjects. Drop-outs may be replaced.

Subjects will undergo a Screening Period of up to 28 days, an approximately two week (Days -1 to 14) Observational Period, followed by three consecutive days of hepatic ultrasound insonification (Days 15, 16 and 17) and a second Observation Period of 11 additional days (Days 18 to 28). The Observational Period is divided in an In-house Period and an Outpatient Visit (OPV). For eligible subjects with a BMI > 35.0 and ≤ 40.0 kg/m² and/or a waist circumference > 40 and ≤ 45 inches, an ultrasound examination will be added to confirm eligibility, and the screening period will be extended for at least 30 days for these subjects.

3.2. Randomization and Blinding

As this is an exploratory, open-label study, no randomization or blinding will be performed and no-unblinding codes are required. If subjects drop out or are removed from the study, they may be replaced until the anticipated number of subjects have completed the study.

3.3. Sample Size Considerations

No formal sample size calculations were performed as this is an exploratory study. The sample size of 15 subjects was empirically determined and consistent with typical sample sizes used for similar exploratory studies to assess robust data.

3.4. Interim Analysis

There are no planned formal interim analyses for this study.

3.5. Timing of Analyses

The final analysis will be performed once all subjects have completed or discontinued the study and the database has been locked.

4. ANALYSIS POPULATIONS/SETS

Safety Population

The Safety population will consist of all subjects who received at least 1 hepatic ultrasound insonification. This will be the primary analysis population for the evaluation of exposure and safety.

Ultrasound Insonification Effect Population

The ultrasound insonification effect population will consist of all subjects who received at least 1 hepatic ultrasound insonification. It is the same as the safety set and will be the primary analysis population for the primary endpoint.

5. GENERAL DATA HANDLING CONSIDERATIONS

All analyses will be conducted using SAS 9.4 or higher.

All data in the database will be presented in by-subject data listings.

Unless otherwise stated, all listings will be sorted by site ID, subject number, and assessment date (and time, if available).

Unless stated otherwise, continuous data will be summarized by number of subjects (n), mean, median, standard deviation (SD), first quartile (Q1), third quartile (Q3), minimum value, and maximum value.

Unless stated otherwise, categorical data will be summarized n and percentage based on the number of non-missing values. Where applicable, the number of missing values will be presented as a separate category with no percentage. Counts of zero will be presented without percentages.

The following precision will be used when presenting data:

- Minimum and Maximum: same number of decimal places as reported in the original data
- Mean, Median, Q1, and Q3: one additional decimal place to that reported for Minimum and Maximum
- SD: two additional decimal places than the Minimum and Maximum
- Percentages: reported to one decimal place
- P-values will be reported to four decimal places. If the value is below 0.0001 it will be noted as < 0.0001; if the value above 0.9999 it will be noted as > 0.9999.

Study data will not be reviewed for purpose of comparison between cohorts/groups. However, if statistical testing is performed, statistical inference will be based on a 5% significance level (i.e. 95% confidence intervals will be produced) and details will be provided in the CSR.

All data up to the time of study completion/withdrawal from the study will be included in the analysis, regardless of duration of treatment.

Numbering for data displays will be based on ICH E3 when applicable.

5.1. Evaluation of Subgroups

There are no formal plans for examining subgroups. If performed, a description will be provided in the CSR.

5.2. Reference Dates

- Screening date is defined as the eCRF provided date on which a subject was screened for trial entry.
- Hepatic ultrasound insonification (HUI) date is defined, for each subject, as the date of first on study HUI.
- Study end date is defined as the subject's date of last study visit or date lost to follow-up.
- Safety data, such as AEs and laboratory assessments will use the subject's first HUI date as a reference date.
- Study day will be defined, in days, relative to each subject's first HUI date.

5.3. Study Day and Duration Variables

For each subject, reference date calculations will generally be defined as the following, assuming non-missing dates:

- date of interest – reference date + 1 when the date of interest \geq reference date;
- otherwise, date of interest – reference date.

If either date is missing, reference date calculations will not be performed. Date imputation will be performed as identified in Section 5.5.

Study day based on first HUI date as the reference would either have a negative value if collected before HUI or a positive value if collected on or after the day of first HUI; there will be no study day zero.

Duration of time is dependent on reference dates and will be calculated in a manner similar to that of the reference date calculation, assuming that dates of interest will strictly follow reference dates (e.g. no negative values).

5.4. Baseline, Post-Baseline Changes, and Last Observed Value (LOV)

Unless stated otherwise, baseline and post-baseline change values will be based on the following:

Baseline will be based on the last non-missing value collected prior to the first on study HUI. Post-baseline values will be those collected after initiation of the first HUI.

Change from baseline is defined as: value – baseline value.

Percent change from baseline is defined as: $[(\text{value} - \text{baseline value})/\text{baseline value}] \times 100\%$.

5.5. Imputation of Partial Dates

Adverse Device Effects (ADE) and Concomitant Medications

- If the start date is completely missing, no imputation will be conducted.
- If the start date is missing day and month, do the following:
 - If the start year does not fall in the same year as that of the HUI date or if the record contains information to indicate that the event ended before the HUI date (e.g. the event end date month and year are earlier than the HUI date or the full end date is known and occurs earlier than the HUI date), then set the start month and day to January 1st.
 - Otherwise, set the start date to the HUI date.
- If only the start day is missing, do the following:
 - If the start month and year does not fall in the same month and year as that of the HUI date or if the event contains information to indicate that the event ended before the HUI date, then set the start day to the 1st day of the month of the event start date.

- Otherwise, set the event start date to the HUI date.
- Event end dates will not be imputed.

These imputation rules will be applied similarly to ADE and concomitant medication dates.

5.6. Multiple Assessments and Visit Windows

Nominal visits (e.g. those identified by the study CRF) will be the basis of summarization and statistical analysis; no visit date windowing will be conducted. Unscheduled data may be included in summaries of most extreme and baseline, summaries of specific abnormalities any time post-baseline, and subject data listings.

5.7. Missing Data

AE and concomitant medication date imputations are described in Section 5.5. Otherwise, missing data will not be imputed for any endpoint or analysis.

6. ANALYSIS METHODS

6.1. Subject Disposition

Summaries of analysis population membership and final subject status (completed or withdrawn), including reasons for withdrawal, will be produced. The number of subjects screened will be provided.

Screen failures, analysis populations, and final subject disposition status will be listed.

6.2. Protocol Deviations

Protocol deviations will be identified and classified as important, important due to COVID-19 pandemic, not important, or not important due to COVID-19 pandemic.

Protocol deviations will be summarized by category. A listing of protocol deviations will be provided.

6.3. Demographic and Baseline Characteristics

Demographic and baseline characteristics will be summarized for all subjects. Summary statistics will be generated for continuous variables (e.g., age and weight) and the number and percentage of subjects within each category will be presented for categorical variables (e.g., gender).

The following variables will be summarized:

- Age as a continuous variable

- Gender
- Ethnicity
- Race
- Baseline Height
- Baseline Weight
- Baseline Waist Circumference
- Baseline Body Mass Index (BMI)
- Tobacco/nicotine use
- Marijuana use
- Alcohol use
- Illicit drug use

The following conversions and equations will be used as applicable:

- Height (in cm) = height (in meters) * 100
- Weight (in kg) = weight (in lbs) * 0.4536
- BMI (kg/m²) = weight(kg)/[height(m)²]
- BSA(m²) = $\sqrt{[(\text{height(cm)} * \text{weight(kg)})/3600]}$

6.4. Medical History

Medical history data will be coded based on the Medical Dictionary for Regulatory Affairs (MedDRA) for reporting by system organ class (SOC) and preferred term (PT). A summary of medical history will be prepared and all medical history data will be presented in a data listing.

6.5. Prior and Concomitant Medication

The incidence of medication use will be summarized by WHO Drug Dictionary anatomic therapeutic class (ATC) Level 2 classification (i.e. therapeutic main group) and preferred name. A subject will be counted only once at each level of reporting. Prior medications are those which have been identified to have been discontinued prior to the treatment start date (e.g. taken exclusively during the pre-therapy period). Concomitant medications are those which have been identified to have been taken at any point during the on-therapy or post-therapy periods. Prior and concomitant medication use will be summarized separately and presented by treatment group.

All prior and concomitant medication data will be listed including the verbatim and preferred drug name and ATC Level 2.

6.6. Device Exposure

Listings of all device exposure data will be produced.

6.7.Two-Step Hyperinsulinemic-Euglycemic Clamp Analysis Parameters

The analysis of the two-step H-E Clamp will consist of summarizing whole-body insulin sensitivity and EGP results. Results will be summarized descriptively and described in the appropriate sections below.

Changes in insulin sensitivity will be assessed by the following calculations:

- SI_{clamp} : Insulin Sensitivity Index
- M: Glucose disposal rate during steady state
- MCR: Glucose metabolic clearance rate during steady state
- M/I: Glucose metabolism: insulin ratio during steady state

The steady-state period for insulin sensitivity measurements is defined as the time from 150 to 180 minutes following the initiation of the continuous insulin infusion during each step, and the GIR recorded during the last 30 minutes (steady-state) of each insulin infusion step is used for the determination of insulin sensitivity. Blood samples for the determination of plasma glucose will be drawn at scheduled time points before and during the clamp.

The insulin sensitivity index (SI_{clamp}) will be calculated from the H-E Clamp data using the formula below, with Step 1 indicating the first phase of the clamp, or the period of administration of the first (lower) insulin infusion rate and Step 2 indicating the second phase of the clamp or the period of administration of the second (higher) insulin infusion rate. Mean glucose infusion rates and mean insulin concentrations will be calculated during steady state (the last 30 minutes of the clamp step) for the applicable step(s).

$$SI_{clamp} = \frac{mean(GI)Step2 - mean(GIR)Step1}{[mean(I)Step2 - mean(I)Step1] \times [mean(BG)Steps1&2]}$$

Change from baseline (CFB) of SI_{clamp} will then be computed for each subject as

$$CFB(SI_{clamp}) = SI_{clamp2} - SI_{clamp1},$$

where clamp 2 is the second clamp and clamp 1 is the first clamp (completed on Day 2; prior to first insonification). Change from baseline of SI_{clamp} , together with SI_{clamp} for each clamp individually, will be included in the efficacy analysis dataset.

Glucose disposal rate (M) during steady state

Glucose disposal rate (M) is obtained as the glucose infusion rate per min corrected for body weight and/or fat free mass. Glucose disposal rate will be calculated separately for Step 1 and Step 2 and for each clamp as the average of the glucose infusion rate per min corrected for body weight and/or fat free mass during the last 30 minutes of the clamp step. The values calculated for Step 1 and Step 2 during the clamp procedure on Day 2 will serve as baseline values and will be compared to the respective Step 1 and Step 2 values on Day 17.

Glucose metabolic clearance rate (MCR) during steady state

Glucose metabolic clearance rate (MCR) is calculated using the formula below for each clamp. Rates will be compared. Glucose MCR will be calculated separately for Step 1 and Step 2, with Step 1 indicating the first phase of the clamp, or the period of administration of the first (lower) insulin infusion rate and Step 2 indicating the second phase of the clamp or the period of administration of the second (higher) insulin infusion rate. The values calculated for Step 1 and Step 2 during the clamp procedure on Day 2 will serve as baseline values and will be compared to the respective Step 1 and Step 2 values on Day 17.

$$MCR = 100 \times \frac{\text{mean}(M)}{\text{mean}(BG)}$$

Where M is the glucose infusion rate per min corrected for body weight and/or fat free mass and BG is blood glucose.

Glucose metabolism: insulin ratio (M/I) during steady state

Insulin ratio (M/I) will be calculated for each clamp and ratios will be compared. Ratios will be calculated separately for Step 1 and Step 2. This is the preferred measure and primary endpoint. Glucose metabolism: insulin ratio (M/I) is calculated as the glucose disposal rate (M) divided by the insulin concentration (I). The values calculated for Step 1 and Step 2 during the clamp procedure on Day 2 will serve as baseline values and will be compared to the respective Step 1 and Step 2 values on Day 17.

6.8. Primary Endpoints and Analyses

6.8.1. Glucose disposal rate: insulin ratio during steady state (M/I)

M/I calculations are described above. The ratio during steady state will be calculated for each step of each clamp and summarized using descriptive statistics in the Ultrasound Insonification Effect Population.

6.8.2. Endogenous glucose production (EGP)

Fasting EGP

Prior to the two-step H-E Clamp, fasting EGP will be assessed utilizing a low primed-continuous infusion of a stable isotope-labeled glucose. At each blood collection time point time point, plasma glucose enrichments will be measured to determine steady state and to determine fasting EGP using steady-state equations (Steele 1959).

EGP will be summarized using descriptive statistics in the Ultrasound Insonification Effect Population.

Insulin-mediated EGP Suppression

Sponsor: GE Research
Protocol Number: GE-HUI-01
Version and Date: Final v2.0, 30JUN2021

For each clamp, the degree of EGP suppression from the fasting EGP value will be determined during the last 30 minutes point during each step of the two-step H-E Clamp using the following equation:

$$\% \text{ EGP suppression} = 1 - (\text{EGP clamp}/\text{EGP fasting})$$

Partial suppression of EGP during Step 1 is assessed to determine hepatic insulin sensitivity and EGP suppression during Step 2 will be measured to confirm EGP was (near) fully suppressed to allow the determination of extrahepatic insulin sensitivity.

%EGP suppression will be summarized using descriptive statistics in the Ultrasound Insonification Effect Population.

6.8.3. Rate of glucose disappearance (Rd)

Under steady state conditions, the Rate of Glucose Disappearance (Rd) is equal to the Rate of Glucose Appearance (Ra) and under these conditions Ra is calculated from the dilution of plasma [6,6-2H2]glucose during constant infusion of [6,6-2H2]glucose. Rd will be calculated during steady state in the fasting period and during Step 1 and Step 2 of the clamp.

Rd will be summarized using descriptive statistics in the Ultrasound Insonification Effect Population.

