--	---

	
Day 16: Following \geq 10 hour overnight fast, in the morning of Day 16, subjects will undergo the second of three ultrasound insonifications. Thereafter, an OGTT will be performed over 180 min. Standardized meals will be provided following the OGTT and in preparation of the clamp, that will be performed on the next day. Approximately around/after 22:00 h, subjects will receive a low-dose IV infusion of insulin to titrate the BG to a target level of 100 mg/dl (\pm 10%) in preparation for the H-E clamp. Approximately at midnight, a primed-continuous IV infusion of stable isotope labeled glucose will also be initiated for the measurement of EGP.
 
Day 17: Following \geq 10 hour overnight fast, in the morning of Day 17, subjects will undergo the last of three ultrasound insonifications. All insonifications will be performed around the same time on each day. Subjects will be monitored for any evidence of hypoglycemia, liver injury, or any other device related adverse effect.
 
Thereafter, subjects will undergo fasting EGP measurements and a 6-hour H-E clamp. During the clamp procedure, IV infusion with stable isotope labeled glucose will be continued to assess EGP suppression at Step 1 and Step 2 of the clamp.
 
Following the glucose clamp, subjects will be monitored post clamp to ensure adequate glycemic stabilization. Subjects will receive a standardized meal at the end of the procedure.
 
Day 18: Blood samples will be taken in the fasting state for safety assessments, metabolic parameters as well as for banking for exploratory biomarkers. A sensor change of the CGMS device will be performed.
 
Subjects may be released home or may be asked to stay in-house for an extended time, if deemed appropriate and needed by the Principal Investigator to monitor for the risk of hypoglycemic episodes.
 
Telephone Visits: Subjects will be contacted every other day until the Follow-up Visit, to remind the subjects of their diet /exercise and to check subjects BG.
 
Outpatient Visit(s):
 
Subjects will check-in on Day 22 for their outpatient visit. A urine pregnancy test (if applicable), and urine drug screen and alcohol breath test will be collected. Blood samples will be taken for safety assessments. Subjects will be re-instructed on maintaining their regular diet and physical activity.
 
Follow-up Visit:
 
A Follow-up Visit will be performed on day 28 for final safety procedures, blood sampling in fasted state for safety, metabolic parameters as well as for banking for future exploratory biomarkers will be performed. A urine pregnancy test (if applicable), and urine drug screen and alcohol breath test will be collected. CGM data will be uploaded to site computer via USB transfer from CGM receiver.

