9.1.20 Overnight IV Insulin Infusion

At approximately 22:00 pm on the evening prior to a clamping procedure, an overnight IV insulin infusion to achieve plasma glucose levels of approximately 100 ± 10 mg/dL during the last two hours of the overnight IV infusion prior to the fasting EGP assessment period. Glucose levels will be monitored frequently.

On the evening prior to the clamp procedure, subjects will receive a standardized dinner, which will be followed by an approximately 10-hour overnight fast.

The aim is to only use insulin to achieve the target glucose level and to avoid simultaneous infusion of glucose. In case blood glucose levels are lower than the target level, an IV glucose infusion may be used and recorded.

The amount of insulin administered will be recorded and expressed in mU/m²/min for each individual subject considering his/her body surface area. GIR will be recorded during the entire clamp procedure.

For details please see the Operations Manual.

9.1.21 Intravenous Infusion of Stable Isotope Labeled Glucose and Assessment of Endogenous Glucose Production

Endogenous glucose production or EGP will be measured in the fasting state prior to the start of the clamp and during the 2-step H-E clamp procedure to assess insulin-induced suppression of EGP using a stable isotope labeled glucose ($[6,6-^2\text{H}_2]$ glucose) tracer method.

A primed-continuous IV infusion of [6,6-²H₂]glucose will be initiated prior to the clamp and continued throughout the clamp at various rates. At approximately midnight, 5.5 mg [6,6-²H₂]glucose/kg body weight will be injected (priming dose) over 10 minutes, followed by a constant infusion of 0.05 mg [6,6-²H₂]glucose/kg body weight/min until the end of the fasting EGP assessment period, followed by a rate of 0.025 mg [6,6-²H₂]glucose/kg body weight/min from beginning to end of the Step 1 insulin infusion. The [6,6-²H₂]glucose infusion is discontinued at the end of the Step 1 of the clamp. Blood samples will be taken during the last 30 minutes of the fasting, step 1 and step 2 periods (see Table 9-3). The glucose enrichment in the plasma will be measured using gas chromatography-mass spectrometry (GC-MS). EGP will be calculated during the last 30 minutes of each assessment period from the dilution of the infused stable isotope labeled glucose using the steady-state method of Steele.

For details please see the Operations Manual and Pharmacy Manual.

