9.1.22 Two-step Hyperinsulinemic, Euglycemic Clamp

On the evening prior to the clamp procedure, subjects will receive a standardized dinner, which will be followed by an approximately 10-hour overnight fast.

Subjects will receive an overnight insulin IV infusion to achieve plasma glucose levels of approximately 100 ± 10 mg/dL during the last two hours of the overnight IV infusion prior to the fasting EGP assessment period.

Subjects will be connected to the Biostator prior to the start of the clamp procedure.

During step 1 and step 2 of the clamp procedure, insulin will be infused at two infusion rates each lasting approximately 180 minutes and D20W will be enriched with stable isotope labeled glucose to achieve a stable isotope glucose enrichment comparable to that of plasma in the fasting state (e.g., 2.5 to 3% for plasma [6,6-²H₂]glucose). Insulin will be infused IV by means of a precision pump for 180 min at the following rate:

Step 1: For the Step 1 insulin infusion of the clamp procedures at Day 2, an amount of 10 mU/m²/min will be added to the average insulin infusion rate which was provided per algorithm over the last 2 hours of the overnight infusion. This will be calculated for each individual subject.

For the Step 1 insulin infusion of the clamp procedures at Day 17, the insulin infusion rate should be identical to the rate used at Day 2. It is important that each subject receives the same insulin infusion rate on Day 17 that he/she received on Day 2.

Step 2: After 180 minutes (end of Step 1), the insulin infusion will be increased to 120 mU/m²/min for a further 180 minutes (Step 2) of the clamp for all subjects at Day 2 and Day 17. This will provide supraphysiological insulin concentrations that will near-maximally stimulate glucose disposal. EGP is expected to be near maximally suppressed.

The glucose infusion rate (GIR; 20% v/v) required to maintain arterialized venous blood glucose (glucose oxidase method) at the target level of 100 ± 10 mg/dL will be recorded throughout the clamp. The steady-state period for insulin sensitivity measurements is

defined as the time from 150 to 180 minutes following the initiation of the continuous insulin infusion during each step, and the GIR recorded during the last 30 minutes (steady-state) of each insulin infusion step is used for the determination of insulin sensitivity. Blood samples for the determination of plasma glucose will be drawn at scheduled time points before and during the clamp.

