Insulin infusion rates may be adjusted per PI discretion and discussion.

The clamp procedure will terminate approximately 6 hours after the initiation of Step 1. The insulin infusion will be discontinued after the last blood sample has been collected.

As a background validation with a second methodology for safety, the standardized measurements of the Biostator will be verified on a regular basis using the YSI reference device at approximately every 30 minutes.

All clamp procedures will follow the same schedule.

For details please see the Operations Manual.

Figure 9-2 Schematic of Clamp Procedure

[figure not shown]

Table 9-3 Schedule for Clamp and Tracer

Parameter		Time in Hours of Day (time is approximate)														
	22:00	24:00	8:30	8:40	8:50	9:00	11:30	11:40	11:50	12:00	14:30	14:40	14:50	15:00		
Primed Continuous [6,6- ² H ₂] Glucose Infusion		X	→	→	→	→	→	→	→	X						
Overnight Insulin Infusion Glucose Control	X	X	→	→	→	X										
Step 1 Insulin Infusion (low dose)						X	→	→	→	X						
Step 2 Insulin Infusion (high dose)										X	→	→	→	X		
Dextrose 20% Infusion Enriched With [6,6- ² H ₂] Glucose						X	→	→	→	→	→	→	→	→	X	
Plasma [6,6- ² H ₂] Glucose Enrichment	X*		X	X	X	X	X	X	X	X	X	X	X	X	X	
Glucose			X	X	X	X	X	X	X	X	X	X	X	X	X	
Insulin			X	X	X	X	X	X	X	X	X	X	X	X	X	
FFA/Triglycerides			X	X	X	X	X	X	X	X	X	X	X	X	X	

*Sample may be taken within window of 22:00 h and 24:00 h. It is of importance, that the sample is taken prior to the start of the [6,6-²H₂]glucose infusion.

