12.1.3.2 EGP

Fasting EGP

Prior to the two-step H-E Clamp, fasting EGP will be assessed utilizing a low primed-continuous infusion of a stable isotope-labeled glucose. At each blood collection

time point, plasma glucose enrichments will be measured to determine steady state and to determine fasting EGP using steady-state equations ([Steele 1959](#)).

Insulin-mediated EGP Suppression

For each clamp, the degree of EGP suppression from the fasting EGP value will be determined during the last 30 minutes point during each step of the two-step H-E Clamp using the following equation:

$$\% \text{ EGP suppression} = 1 - (\text{EGP clamp}/\text{EGP fasting})$$

Partial suppression of EGP during Step 1 is assessed to determine hepatic insulin sensitivity and EGP suppression during Step 2 will be measured to confirm EGP was (near) fully suppressed to allow the determination of extrahepatic insulin sensitivity.

Rate of Glucose Disappearance (Rd)

Under steady state conditions, the Rate of Glucose Disappearance (Rd) is equal to the Rate of Glucose Appearance (Ra) and under these conditions Ra is calculated from the dilution of plasma [6,6-²H₂]glucose during constant infusion of [6,6-²H₂]glucose. Rd will be calculated during steady state in the fasting period and during Step 1 and Step 2 of the clamp.

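### The Rd method is tied to a constant tracer infusion that stops before Step 2, and neither analysis section says how the label in the enriched dextrose is counted

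*SAP*

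**What the plan says.** **Analysis sections.** SAP 6.8.3 sets Rd equal to the rate of appearance (Ra) at steady state, and "Ra is calculated from the dilution of plasma [6,6-2H2]glucose during constant infusion of [6,6-2H2]glucose". Protocol 12.1.3.2 describes the same method and adds: "Rd will be calculated during steady state in the fasting period and during Step 1 and Step 2 of the clamp". The SAP names the same three periods. SAP 6.8.2 and protocol 12.1.3.2 give a suppression ratio for EGP and cite steady-state equations for fasting EGP. Neither prints an equation for Ra or for EGP during the clamp.

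**Constant tracer infusion.** Protocol 9.1.21 gives 0.05 mg/kg/min until the end of the fasting assessment and 0.025 mg/kg/min during Step 1. It then says that the tracer "infusion is discontinued at the end of the Step 1 of the clamp". Table 9-3 also ends it at about 12:00, when Step 2 starts. Earlier in the same paragraph, 9.1.21 describes the primed-continuous infusion as "continued throughout the clamp at various rates".

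**Second tracer source.** Protocol 9.1.22 says that during both steps "D20W will be enriched with stable isotope labeled glucose", so that plasma enrichment stays near its fasting level (2.5–3% is the example). Table 9-3 has a separate row for it, "Dextrose 20% Infusion Enriched With" the tracer, running through Step 1 and Step 2. The SAP never mentions labelled dextrose.

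**Broader wording.** For EGP, protocol 9.1.21 takes the last 30 minutes "of each assessment period from the dilution of the infused stable isotope labeled glucose". The study summary for Day 17 says that "IV infusion with stable isotope labeled glucose will be continued to assess EGP suppression at Step 1 and Step 2 of the clamp", without saying which infusion is meant.

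**The concern.** The condition that the SAP attaches to the Rd calculation is not met in one of the three periods where Rd is required. In Step 1 it is met, but it covers only part of the label reaching the subject. The rest arrives with the dextrose, at a rate that follows the GIR. An analyst working from the SAP alone would use the constant rate as the numerator; one who knows the procedures would add the dextrose label. The same data then give two different Rd values.

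Rd and EGP are two of the three listed primary endpoints, and both are to be read as changes from Day 2 to Day 17. Protocol 6.3 gives the separation of hepatic from peripheral insulin sensitivity as the reason for combining the tracer with two insulin steps. A numerator that omits a GIR-dependent term undermines that separation, because its error shifts whenever GIR shifts between the two clamps.

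**Working it through.** The plan gives no Rd or EGP figure to reproduce, so the check is a tracer balance.

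**Inputs from the protocol**
- F, constant tracer rate: 0.05 mg/kg/min fasting, 0.025 in Step 1, none in Step 2 (9.1.21, Table 9-3).
- Plasma enrichment aimed at: 2.5–3% (9.1.22).

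**Assumed, because the documents do not give them**
- Einf, enrichment of the dextrose: 2.5–3%, taken from the plasma target.
- GIR and clamp EGP: ranges as shown, in mg/kg/min.

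**Formulas** (enrichment as tracer/tracee; Ep is plasma enrichment)
- Ep = (F + GIR × Einf) / (EGP + GIR)
- All label counted: Ra = (F + GIR × Einf) / Ep
- Constant infusion only: Ra = F / Ep
- Shortfall of the second against the first: GIR × Einf / (F + GIR × Einf)

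**Fasting.** No labelled dextrose is running, so both versions agree. As a consistency check, 0.05/0.03 = 1.67 and 0.05/0.025 = 2.0 mg/kg/min.

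**Step 1 shortfall, F = 0.025**

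| GIR | Einf 2.5% | Einf 3% |
|---|---|---|
| 0 | 0% | 0% |
| 0.5 | 0.0125/0.0375 = 33% | 0.015/0.040 = 38% |
| 1.5 | 0.0375/0.0625 = 60% | 0.045/0.070 = 64% |
| 3 | 0.075/0.100 = 75% | 0.090/0.115 = 78% |
| 5 | 0.125/0.150 = 83% | 0.150/0.175 = 86% |

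**Step 2.** With F = 0, constant infusion only gives 0/Ep = 0 at any GIR. With all label counted, GIR 8, EGP 0.3 and Einf 2.75% give Ep = 0.22/8.3 = 0.02651, Ra = 0.22/0.02651 = 8.30 and EGP = 8.30 − 8 = 0.30, as put in.

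**Change from baseline, Step 1, Einf 2.5%** (illustration)
- Day 2, EGP 1.0, GIR 1.0: true Ra 2.0; Ep = 0.050/2.0 = 0.0250; F/Ep = 1.00.
- Day 17, EGP 0.7, GIR 2.0: true Ra 2.7; Ep = 0.075/2.7 = 0.0278; F/Ep = 0.90.
- A true rise of 0.7 (35%) reads as a fall of 0.10 (10%). The error does not cancel.

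**Would the error be seen?** At steady state Rd cannot be below GIR. F/Ep falls below GIR once GIR exceeds √(F × EGP/Einf):
- EGP 0.5, Einf 3%: √(0.025 × 0.5/0.03) = 0.65.
- EGP 1.4, Einf 2.5%: √(0.025 × 1.4/0.025) = 1.18.

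Over that EGP range, any GIR above 1.18 gives an impossible Step 1 Rd. The Day 17 value above, 0.90 against a GIR of 2.0, is one.

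**The case against.** The best reply is that the protocol already implies the correct method. Section 9.1.21 calculates EGP in every assessment period from the infused label, and with the constant infusion stopped, the labelled dextrose is the only label infused in Step 2. EGP there can be obtained only by counting it. EGP and Rd come from the same Ra, so counting the dextrose label for one and leaving it out of the other would be incoherent. On this view SAP 6.8.3 states a general principle and does not list tracer sources. Section 9.1.21 also refers to an Operations Manual and a Pharmacy Manual, which are not part of the public documents and may contain the equation. The study summary's statement about Step 2 is true of the labelled dextrose. Finally, this is an exploratory pilot of about 15 subjects with descriptive summaries.

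Much of this stands. A reader might infer that the trial would report wrong Rd values without anyone noticing; the documents do not support that. Zero in every subject in Step 2, and Rd below GIR in Step 1 at moderate GIR, would alert a competent analyst.

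The reply does not remove the gap. The helpful sentence sits in a procedures section, covers EGP only, and does not say how the dextrose label or the infused glucose enters. Protocol 12.1 assigns the detail of variables and methods to the SAP, and the SAP's own sentence cannot be applied to Step 2 as written. Noticing an impossible value also does not settle which equation was prespecified.

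**Conclusion.** The Rd rule in SAP 6.8.3 and protocol 12.1.3.2 conflicts with the protocol's own tracer schedule, and clamp EGP has no stated equation. Taken literally, the rule makes Step 2 Rd not estimable and understates Step 1 Rd by 33–38% at a GIR of 0.5 and 75–78% at 3 mg/kg/min, with no error at a GIR of 0. These sizes rest on F = 0.025 from the protocol, the 2.5–3% plasma target used as the dextrose enrichment, and assumed GIR values. They are what the literal reading would produce, not an expected bias in the results.

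The Step 2 result rests on the constant infusion ending with Step 1, which 9.1.21 and Table 9-3 both state. If it ran on, as the other phrase in 9.1.21 suggests, Step 2 Rd would be understated by the same formula.

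A reader might also infer that every primary endpoint is compromised. That is not so: M/I, which SAP 6.7 singles out among the primary measures, uses GIR and insulin only, and fasting EGP and fasting Rd involve no labelled dextrose. The point is worth correcting because it concerns how two listed primary endpoints are calculated during the clamp, and the correction is short.

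**What to change.** In SAP 6.8.2–6.8.3 and protocol 12.1.3.2, replace the reference to a constant infusion with wording that counts all infused tracer, and state for each period:

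- Ra = (F + GIR × Einf) / Ep, where F is the constant tracer rate actually given in that period (0 if stopped), Einf the recorded dextrose enrichment, and Ep the mean plasma enrichment over the last 30 minutes.
- Rd = Ra at steady state.
- EGP = Ra minus exogenous glucose: Ra − GIR with tracer/tracee enrichment and GIR as unlabelled dextrose; Ra − GIR − F with tracer/total enrichment and GIR as total dextrose.
- One definition of enrichment, used for both Einf and Ep.

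Reconcile the two statements in protocol 9.1.21 on how long the tracer infusion runs, and have the study summary name which labelled infusion continues in Step 2. If the analysis has already been run, the study report should state the equation used.

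**Cost.** This needs text changes and no new subjects, visits or plasma samples, because GIR and plasma enrichment are already collected. The real demand is that dextrose enrichment be recorded or assayed per batch, since Step 2 EGP is a small difference between large terms. At an assumed Step 2 GIR of 4–8 mg/kg/min with EGP near 0, a 3% relative error in Einf moves Step 2 Rd and EGP by 0.03 × 4 = 0.12 to 0.03 × 8 = 0.24 mg/kg/min. Against fasting EGP of 2.0 and 1.67 respectively, that is 0.12/2.0 = 6 to 0.24/1.67 = 14 percentage points of EGP suppression.
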